Effective date: 2017-08-17 12:21

Effective

Version: 4.0

 GALDERMA	Title 43USK1701 CIP	Doc id [REDACTED]
---	-------------------------------	----------------------

A Randomized, Controlled, Evaluator-Blinded, Multi-Center Study to Evaluate the Effectiveness and Safety of *Restylane® Kysse* versus a Control in the Augmentation of Soft Tissue Fullness of the Lip

Study product: *Restylane® Kysse*

Comparator product: [REDACTED]

Clinical trial number (CTN): 43USK1701

Sponsor: [REDACTED]

Investigators and Study Administrative Structure

Sponsor:

Q-Med AB, a Galderma affiliate

Galderma Research and Development, LLC

Medical Expert:

Clinical Project Manager:

Study Statistician:

Further details on all participating Investigators and the complete administrative structure of the study are found in the study files. Note that administrative changes are to be documented in the study files without requiring a clinical investigational plan (CIP) amendment.

Sponsor Signatures

The CIP is electronically signed in the document management system within the Q-Med AB quality management system by the representatives listed below.

[REDACTED]

[REDACTED] [REDACTED]

[REDACTED] [REDACTED]

[REDACTED]

[REDACTED]

[REDACTED] [REDACTED] [REDACTED]

[REDACTED]

[REDACTED]

[REDACTED]

Synopsis

Title of study:	A randomized, controlled, evaluator-blinded, multi-center study to evaluate the effectiveness and safety of Restylane® Kysse versus a control in the augmentation of soft tissue fullness of the lip
Clinical Trial Number:	43USK1701
Countries involved	United States
Number of sites	Approximately 15
Number of Subjects	Approximately 280 randomized subjects. [REDACTED]
Target Indication	Injection into the lips for lip augmentation and for correction of perioral rhytids in subjects over the age of 21.
Primary Effectiveness Objective and Endpoint	1. The primary objective of the study is to demonstrate non-inferiority of Restylane® Kysse versus a control in lip fullness augmentation by comparing change from baseline in the Blinded Evaluator assessment of Medicis Lip Fullness Scale (MLFS) in the upper and lower lip separately, at 8 weeks after last injection.
Secondary Effectiveness Objectives and Endpoints	1. To evaluate the effectiveness of Restylane® Kysse in lip fullness augmentation based on the Blinded Evaluator assessment of MLFS in the upper and lower lip, using the following endpoints: 
 Change from baseline at 16, 24, 32, 40, and 48 weeks after last injection Response rates (defined as at least 1 point improvement from baseline) at 8, 16, 24, 32, 40, and 48 weeks after last injection. 2. To evaluate the aesthetic improvement of the upper perioral rhytids and oral commissures after treatment with Restylane® Kysse , based on the Blinded Evaluator assessment of Wrinkle Assessment Scale ¹ (WAS), at 8, 16, 24, 32, 40, and 48 weeks after last injection using the following endpoints: 
 Change from baseline Response rates (defined as at least 1 point improvement from baseline). 3. To evaluate the aesthetic improvement (overall appearance)

¹Lemperle, G. A Classification of Facial Wrinkles. Plastic Reconstructive Surgery. 2001:1735-1750.

	
after treatment with Restylane® Kysse, based on the Global Aesthetic Improvement Scale (GAIS) at Week 8, 16, 24, 32, 40, and 48 weeks after last injection using response rates (defined as at least “Improved”).
 
4. Subjects’ satisfaction after treatment with Restylane® Kysse using the FACE-Q scales Satisfaction with Lips and Appraisal of Lines: Lips at Week 8, 16, 24, 32, 40, and 48 weeks.5. Lip fullness compared to baseline, using Central Independent Photographic Reviewer’s assessment of improvement in fullness of each (yes/no) by comparison of random, blinded pairings of the baseline and post-baseline photographs taken at Week 8, 24, 40, and 48.
Safety Objectives and Endpoints	
1. To evaluate all adverse events (AEs) and pre-defined, expected, post-treatment events reported during the first 4 weeks after treatment as recorded in the subject diary.2. To evaluate the safety assessment at all visits, as assessed by a qualified staff member:
• Presence of any unexpected resistance by palpation of each lip at baseline and at each physical follow-up visit.• Lip texture and symmetry according to pre-defined methods, for each lip at baseline and at each physical follow-up visit.• Lip movement, function, and sensation (on three different locations per lip) according to pre-defined methods, at baseline and at each physical follow-up visit.
	 A large rectangular area of the page is completely blacked out, indicating redacted content. The redaction is approximately 85% of the page width and 85% of the page height.

Study Design	Randomized, evaluator-blinded, controlled, parallel group, multi-center, US study
Subject Participation	A subject will be involved in the study for approximately 15 months from screening to final follow-up visit.
Enrollment	Written informed consent will be obtained before any study related procedure is performed. Subjects will be screened for eligibility within 30 days prior to injection. The screening visit and baseline visit may be performed on the same day. Subsequent to screening, eligible subjects will be randomized in the study. [REDACTED]
	At least 42 subjects will be Fitzpatrick skin type IV through VI. [REDACTED]
Treatment	Initial Treatment The subjects will be randomized (2:1) to receive either Restylane® Kysse or Juvéderm Volbella® XC in both lips on Day 1. [REDACTED] Treatment of the upper perioral lines, vermillion border, philtral columns, cupid's bow, and/or oral commissures may be performed to obtain optimal aesthetic result, as agreed by the Treating Investigator and subject. [REDACTED] [REDACTED]

[figure not shown]
Study Procedures	
	
Evaluation of safety
 
Adverse Events (AEs) will be obtained from signs and symptoms reported by the subject or detected during each examination visit to obtain information about any medical occurrence that meets the definition of an AE. In addition, all subjects will complete a Diary for 4 weeks after each treatment, to collect information about pre-defined, expected, post-treatment events at the treated area. Any subject with a treatment related AE that is ongoing at the time of study completion will be followed until that AE is resolved or stabilized. Any AE assessed as related to the study product or injection procedure with onset after subject participation in the study is over, and that the Investigator becomes aware of should be reported to the Sponsor.

	
Study report
 
A study report will be compiled at the conclusion of the study. This report will be included in the regulatory submission for marketing application.

Inclusion criteria:	
1. Subjects willing to comply with the requirements of the study and providing a signed written informed consent.2. Males or non-pregnant, non-breastfeeding females, 22 years of age or older.3. Subjects seeking augmentation therapy for the lips.

Exclusion criteria:	1. Known/previous allergy or hypersensitivity to any injectable HA gel or to gram positive bacterial proteins. 2. History of allergy or hypersensitivity to lidocaine or other amide-type anesthetics, or topical anesthetics or nerve blocking agents (if such products are intended to be used for that subject).		

25. Participation in any interventional clinical study within 30 days of screening.

Investigational product:	Restylane® Kysse injectable gel. [REDACTED]
Reference therapy	Juvéderm Volbella® XC injectable gel. [REDACTED]
Therapy Dose	[REDACTED]
Schedule of Events	[REDACTED]
Efficacy Assessment:	[REDACTED]

Safety Assessment:	
	
Statistical Methods:	
Sample size A maximum of 280 subjects will be treated in the study. 
 
Principles for the Analysis In general, all effectiveness, safety and baseline characteristics variables will be presented using descriptive statistics within each treatment group, and graphs as appropriate. Continuous endpoints will be summarized using descriptive statistics, e.g. mean, median, standard deviation, minimum and maximum values. Categorical endpoints will be presented in frequency tables with number and percentage of observations for each level.

Abbreviations and Definitions of Terms

AE	Adverse event
BDDE	1,4-butanediol diglycidyl ether
CE	“Conformité Européenne” the quality and branding mark for products made or sold within the European Union.
CFR	Code of Federal Regulations
CIP	Clinical Investigational Plan
Childbearing Potential	The ability of a pre-menopausal female to become pregnant. This includes women using oral, injectable or barrier contraception; women who have had a tubal ligation; women who are single; and women whose male partners have been vasectomized or utilize barrier contraceptive methods.
CTA	Clinical trial agreement
CTN	Clinical trial number
CV	Curriculum vitae
Device deficiency	Inadequacy of a medical device with respect to its identity, quality, durability, reliability, safety or performance (includes malfunctions, use errors, and inadequate labelling)
DMP	Data management plan
eCRF	Electronic case report form
ET	Early termination
FDA	United States Food and Drug Administration
First subject in	First subject screened, i.e. who signs the informed consent form
First subject out	First subject who completed their last study visit
FST	Fitzpatrick Skin Type
G	Gauge
GCP	Good clinical practice
HA	Hyaluronic acid
HIPAA	Health Insurance Portability and Accountability Act
ICH	International Conference on Harmonization
IFU	Instructions for use
Investigational Product	Medical device being assessed for safety or performance in a study. “Investigational product” is the same as “study device”, “investigational device”, or “investigational medical device”.

Institution	Any public or private entity or agency or medical or dental facility where a clinical study is conducted.
Investigator	The Principal Investigator (PI) or other qualified person, i.e. sub-investigator, designated and supervised by the PI at a study site to perform critical study-related procedures or to make important study-related decisions as specified on the signature and delegation log
Investigator file	Essential documents relating to a clinical study as defined in applicable GCP guidance document and maintained by the Investigator.
██████████	██████████
IRB	Institutional review board
ISO	International Organization for Standardization
ITT	Intention-to-treat
Last subject in	Last subject who entered the study
Last subject out	Last subject who completed their last study visit
MedDRA	Medical dictionary for regulatory activities
██████████	██████████
NSAID	Non-steroidal anti-inflammatory drugs
PI	Principal Investigator; qualified person responsible for conducting the study at a study site
PP	Per protocol
PT	Preferred term
QA	Quality assurance
RA	Regulatory authority
ROPI	Report of Prior Investigations, i.e. compilation of the current clinical and non-clinical information on the investigational product, relevant to the clinical study
SAE	Serious adverse event
SAP	Statistical Analysis Plan
SDV	Source data verification
SOC	System Organ Class
Sponsor file	Essential documents relating to a clinical study as defined in applicable GCP guidance document and maintained by the Sponsor.
Study files	The Investigator file and the Sponsor file
Study products	The investigational product and the reference product under study
Study site	Institution or site where the study is carried out
TC	Telephone Call

Touch-up Repeated injection to be performed after treatment if necessary to achieve optimal correction

Tx

Treatment

WAS

Wrinkle Assessment Scale

WHO

World Health Organization

Table of Contents

INVESTIGATORS AND STUDY ADMINISTRATIVE STRUCTURE	2
SIGNED AGREEMENT OF THE CLINICAL INVESTIGATIONAL PLAN	4
SYNOPSIS	5
ABBREVIATIONS AND DEFINITIONS OF TERMS	16
LIST OF TABLES	22
LIST OF FIGURES	22
LIST OF APPENDICES	22
ETHICAL CONSIDERATIONS	23
1.1 Statement of ethical compliance	23
1.2 Application to independent ethics committee and/or regulatory authorities	23
2. BACKGROUND INFORMATION	23
2.1 Indication and population description	23
2.2 Investigational and comparator product descriptions	23
2.2.1 Clinical documentation	24
2.3 Study rationale	24
2.4 Justification for the design of the study	25
2.5 Risks and benefits	25
3. OBJECTIVE(S) AND ENDPOINT(S)	26

List of Appendices

Ethical Considerations

1.1 Statement of ethical compliance

The study shall be conducted in compliance with the clinical trial agreement, the clinical investigational plan, good clinical practice (GCP), and applicable regional or national regulations. The international standard for clinical study of medical devices for human subjects, ISO14155 shall be followed. The International Conference on Harmonization (ICH) guideline for GCP (E6) shall be followed as applicable for medical device. The study shall be conducted in accordance with the ethical principles that have their origin in the Declaration of Helsinki

1.2 Application to independent ethics committee and/or regulatory authorities

It is the responsibility of the Principal Investigator (PI) to obtain approval of the CIP/CIP amendment(s) from the institutional review board (IRB). The study shall not begin until the required favorable opinion from the IRB has been obtained. The PI shall file all correspondence with the IRB in the Investigator file and copies of IRB approvals shall be forwarded to the Sponsor. Any additional requirements imposed by the IRB or regulatory authorities (RA) shall be followed.

The study requires application for approval from the US Food and Drug Administration (FDA). The study will not be started until the Sponsor has received written approval or until the statutory waiting period from the appropriate authority has elapsed.

The collection, access to, processing, and transfer of protected health information or sensitive personal data shall be carried out in accordance with applicable rules and regulations.

2. Background Information

2.1 Indication and population description

2.3 Study rationale

The rationale of performing this study is to obtain evidence of safety and effectiveness of *Restylane® Kysse* to support a future US marketing application.

2.5 Risks and benefits

3. Objective(s) and Endpoint(s)

3.1.1 Primary objective and endpoint

The primary objective of the study is to demonstrate non-inferiority of *Restylane® Kysse* versus a control in lip fullness augmentation

3.1.2 Secondary objectives and endpoints

The secondary objectives and endpoints are:

- To evaluate the effectiveness of *Restylane® Kysse* in lip fullness augmentation
- To evaluate the aesthetic improvement of the upper perioral rhytids and oral commissures after treatment with *Restylane® Kysse*,
- To evaluate the aesthetic improvement (overall appearance) after treatment with *Restylane® Kysse*,

¹Lemperle, G. A Classification of Facial Wrinkles. Plastic Reconstructive Surgery. 2001;1735-1750.

3.1.3 Safety objectives and endpoints

The safety objectives and endpoints are:

- To evaluate all AEs at all visits and pre-defined, expected, post-treatment events reported during the first 4 weeks after treatment as recorded in the subject diary.
- To evaluate the safety assessment at all visits, as assessed by a qualified staff member:

4. Design of the Study

4.1 General outline

This is a randomized, controlled, evaluator-blinded, multi-center study to evaluate the effectiveness and safety of *Restylane® Kysse* for lip augmentation and correction of perioral rhytids. Approximately 280 subjects will be randomized in a 2:1 ratio of treatment to control and treated. Approximately 187 subjects will be treated with *Restylane® Kysse* and 93 subjects will receive the control in the lips and perioral rhytids for 48-weeks. All randomized subjects' lips will have a MLFS score of 1 (Very Thin) or 2 (Thin). The upper lip and lower lip scores do not have to be equal as long as each score is 1 or 2.

At least 42 subjects enrolled and treated will be FST IV through VI. This includes up to 21 subjects with FST V to VI who do not have to meet the inclusion criteria for MLFS.

Investigator blinding will be accomplished by using a Treating Investigator to administer the treatments and a Blinded Evaluator, to whom randomization and treatment are concealed, to conduct the blinded assessments. Safety assessments will be performed by non-blinded personnel.

Eligible subjects randomized to receive treatment will be injected by the Treating Investigator at Day 1. The method of injection is at the discretion of the Treating Investigator and will be recorded. Sufficient amount of product should be injected to achieve optimal correction of the lips, in the opinion of the Treating Investigator and subject. Optimal appearance is defined as at least 1 MLFS step improvement from Baseline and best correction that can be achieved as agreed by the Treating Investigator and the subject. Touch-up treatment may be administered after 4 weeks if deemed necessary to obtain optimal aesthetic result; this decision should be agreed upon by the Treating Investigator and the subject. Touch-up treatment will not be performed if the subject has a disease or condition described in the exclusion criteria, or an ongoing treatment-related AE that in the opinion of the Treating Investigator would be worsened by a touch-up. It is recommended that the dose should not exceed 1.5 mL in each lip (including vermillion, vermillion border and cupid's bow) per treatment session. The study product may also be injected for optimal correction of the upper perioral rhytids, philtral columns, and/or oral commissures. The recommended maximum injected volume per subject and treatment is 6 mL (i.e. 3 mL for lips and 3 mL for perioral area).

Subjects will have in-clinic follow up visits at 2, 4, 8, 16, 24, 32, 40, and 48 weeks after the last injection. If a touch-up is performed, a second 2-week and 4-week follow-up visits should be scheduled. At the 48-week visit after all study procedures for the visit are completed, subjects can receive an optional additional treatment if optimal aesthetic improvement is not maintained with *Restylane® Kysse*. If re-treatment is performed, a second 2-week and 4-week follow-up visits should be scheduled. In addition to the clinic visits, phone visits will also occur as specified in the study flow chart below.

A Study Flow Chart is provided on the next page.

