#### 1.1.2 Number of subjects and randomization

Approximately 280 subjects will be randomized to treatment or to control in a 2:1 ratio (treatment: control) stratified by FST (I-III, IV or V-VI) to achieve a total sample size of 234 evaluable subjects

[REDACTED]

Before starting the study, a randomization list will be prepared under the supervision of a designated statistician. Randomization will be performed using an Interactive Response System by assigning each subject to *Restylane® Kysse* or the control according to the randomization list.

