#### 1.2.4 Exploratory objectives

- To evaluate the consistency of the primary analysis results across different subgroups, specifically:
  - Study site
  - Fitzpatrick skin types (I-III and IV-VI)
  - Race
- To evaluate the consistency of AE data across different subgroups, specifically:
  - Study site
  - Injection volume
  - Fitzpatrick skin types (I-III and IV-VI)
- [REDACTED]

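### Do the MLFS exemption in Protocol 4.1 and the pooled skin-type IV–VI group in SAP 1.2.4 need correcting?

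*Protocol*

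**What the plan says.** Protocol 4.1 sets the size and allocation: "Approximately 280 subjects will be randomized in a 2:1 ratio of treatment to control and treated". It then says that all randomized subjects' "lips will have a MLFS score of 1 (Very Thin) or 2 (Thin", and that the two lips may differ as long as each is 1 or 2. The next paragraph sets a minimum of 42 treated subjects with FST IV–VI and continues: "This includes up to 21 subjects with FST V to VI who do not have to meet the inclusion criteria for MLFS". The Synopsis repeats the minimum ("At least 42 subjects will be Fitzpatrick skin type IV through VI") and caps treatment: "A maximum of 280 subjects will be treated in the study".

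The SAP groups skin type in two ways:

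- SAP 1.1.2: randomization is "stratified by FST (I-III, IV or V-VI", three strata.
- SAP 1.2.4: both the primary-result objective and the AE objective ("To evaluate the consistency of AE data across different subgroups, specifically") list "Fitzpatrick skin types (I-III and IV-VI", two groups.
- SAP 2.5.5: related AEs are summarized for I–III, IV and V–VI, three groups.

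Several places that could settle the handling of exempt subjects cannot be read. The visible inclusion list stops at item 3, and Protocol 4.4 on randomization is redacted. The ITT definition in SAP 2.2 and the eligibility bullet for the per-protocol set in SAP 2.3.2 are each redacted in part. SAP 2.4.5, on exploratory efficacy, appears in the contents but its text is not shown.

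**The concern.** Two things look wrong. First, if exempt subjects are randomized, the sentence about all randomized subjects is not literally true. The cap of 280 treated subjects leaves no obvious room for a separate non-randomized cohort, so randomization is the likelier reading. A site or monitor could then find two statements on whether an FST V–VI subject outside MLFS 1–2 may enter.

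Second, only V–VI can contain exempt subjects. A pooled IV–VI row would combine a stratum in which everyone must score 1 or 2 with one in which up to 21 need not. A difference from I–III, or a lack of one, could not then be put down to skin type alone. On AEs the SAP also appears to disagree with itself, because the objective names two groups and the analysis three.

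At stake would be the clarity of an eligibility statement and the reading of some exploratory tables.

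**Working it through.** **The plan's own figures.** SAP 1.1.2 gives 234 evaluable subjects and SAP 2.7 about 15% loss: 234 / (1 − 0.15) = 275.3, so 276, consistent with approximately 280. At 2:1, 280 × 2/3 = 186.7, which gives the stated 187 and 93. These figures reproduce. The SD and power behind 234 are redacted.

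**How large the mixing could be.** Inputs are the ceiling of 21 exempt subjects, the minimum of 42 with FST IV–VI, and the total of 280.

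| Row | Largest exempt share |
|---|---|
| All randomized | 21/280 = 7.5% |
| Pooled IV–VI, n = 42 | 21/42 = 50% |
| Pooled IV–VI, n = 56 (assumed) | 21/56 = 37.5% |
| Pooled IV–VI, n = 70 (assumed) | 21/70 = 30% |
| V–VI alone, n = 21 (assumed) | 21/21 = 100% |
| V–VI alone, n = 30 (assumed) | 21/30 = 70% |

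These are worst cases, since 21 is a maximum and 42 a minimum. With 10 exempt subjects the pooled share at n = 42 is 10/42 = 24%; with 5 it is 5/42 = 12%.

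**What splitting would buy.** For a difference in means, the 95% half-width is t(0.975, n1 + n2 − 2) × SD × √(1/n1 + 1/n2). The documents show no SD, so 0.7 to 1.1 is assumed.

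- Pooled IV–VI, 28 versus 14: 2.021 × SD × 0.3273 = 0.46 (SD 0.7) to 0.73 (SD 1.1).
- V–VI alone, 14 versus 7: 2.093 × SD × 0.4629 = 0.68 to 1.07.

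The non-inferiority margin is 0.5. The split row exceeds it across the whole assumed range, so it could be descriptive only. For AEs, the exact two-sided 95% upper limit when no event is seen is 1 − 0.025^(1/n): 12.3% for n = 28 and 23.2% for n = 14.

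Splitting also does not isolate the exempt subjects, because V–VI may hold subjects who meet the MLFS criterion as well.

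**The passages side by side.**

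1. *Eligibility.* The general rule and the exemption stand in consecutive paragraphs of Protocol 4.1. The exemption names the criterion it lifts, the skin types it covers and its ceiling. A specific exception placed directly after a general rule is read as limiting that rule.
2. *AEs.* SAP 2.5.5 defines the tables and already uses the randomization strata. It lists no pooled IV–VI AE row, so the feared mixing does not arise. Only the wording of the objective in 1.2.4 is out of step.
3. *Primary result.* SAP 1.2.4 states the objective; the analysis belongs in SAP 2.4.5, whose text is not shown and may use either grouping. If exempt subjects are randomized, the arm comparison inside a pooled row is still a randomized one. Mixing affects only the comparison of one skin-type row with another.
4. *Recoverability.* SAP 2.1 provides by-subject listings of the data used in the summaries, and FST is a baseline variable in SAP 2.3.3. Baseline MLFS is needed to derive the primary endpoint. An analyst can therefore count and identify V–VI subjects outside MLFS 1–2 without new data.

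**The case for a change.** The strongest case for a change is that both mismatches are in visible, current text and cost almost nothing to repair: one exception clause in the protocol, and matching FST wording in SAP 1.2.4 with a few rows. No redacted text can make the sentence about all randomized subjects literally true if exempt subjects are randomized. That much stands. It is not proven that they are. Protocol 5.4 counts a subject as enrolled when randomized and/or treated, and the FST sentence in 4.1 speaks of subjects enrolled and treated. The V–VI stratum does not decide it, since V–VI subjects with MLFS 1 or 2 would fill it too. The cap of 280 favours randomization without settling it.

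A weightier argument concerns the primary analysis.

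- If all 21 were counted in the 280 but not evaluable, (280 − 21) × 0.85 = 220, below 234. With a true difference of 0 and one-sided 2.5%, power per endpoint would go from 99.5% to 99.2% at an assumed SD of 0.8, or from 95.0% to 93.8% at SD 1.0.
- If all 21 were in the primary set and showed no arm difference at all, a true difference at the margin would shrink to 0.5 × (1 − 21/280) = 0.4625. The one-sided error per endpoint would rise from 2.5% to about 4.8% (SD 1.0) or 7.1% (SD 0.6).

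These figures need the maximum number of exempt subjects, a handling that the readable text does not state and, in the second case, an extreme response pattern. A lip-fullness effect that is equal in both arms cancels in the difference. Neither rewording Protocol 4.1 nor splitting exploratory rows would alter who is in the analysis set, so these figures do not support the change under discussion.

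**Conclusion.** No change to the plan follows. The sentence in Protocol 4.1 is a general rule with its exception in the next paragraph, and its over-broad wording is a clerical slip. The FST mismatch on AEs is also clerical, because SAP 2.5.5 already reports the three randomization strata. Pooling IV–VI for the primary-result subgroup is a fair trade-off between a mixed row (up to 50% exempt at the minimum of 42) and a V–VI row with a half-width of 0.68–1.07 grade against a margin of 0.5. If the documents are reopened for other reasons, the two sentences in 4.1 can be reconciled and the AE objective in SAP 1.2.4 worded like 2.5.5. Separate IV and V–VI rows, with a count of V–VI subjects outside MLFS 1–2, would be an optional descriptive extra.

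This rests on three things: an assumed SD of 0.7–1.1, worst-case counts of exempt subjects, and the exemption being read as governing. How exempt subjects enter the ITT and per-protocol sets cannot be judged from the readable text. On that text, no effect is shown on the primary test or on who is treated.

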### 2.2 Analysis Populations

The following populations will be defined for analysis:

- **Safety population:** Includes all subjects who received any of the investigational products, based on the as treated principle (i.e. according to the treatment actually received).
- **Intention-to-treat (ITT) population:** Includes all subjects who were randomized [REDACTED] All ITT analyses will be based on the as randomized principle (i.e. according to the treatment they were randomized to).
- **Per protocol (PP) population:** Includes all subjects in ITT who complete the Week 8 visit without any deviations considered to have substantial impact on the primary effectiveness outcome.

The primary efficacy analysis of non-inferiority will be performed both on the ITT and the PP analysis set. Secondary effectiveness and all safety evaluations will be performed based on the ITT and the safety population set, respectively.

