## 2.7 Determination of Sample Size

[REDACTED]. Accounting for approximately 15% drop-outs and non-evaluable subjects due to protocol deviations at week 8, a total of approximately 280 subjects will be randomized in the study. It is expected that the number of randomized subjects will be similar across the study sites.

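### Do the up to 21 FST V–VI subjects exempt from the MLFS entry criterion bias the non-inferiority test or undercut the 234 evaluable subjects?

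*Protocol*

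**What the plan says.** Protocol 4.1 gives a rule and then an exception. The rule is that all randomised subjects' "lips will have a MLFS score of 1 (Very Thin) or 2 (Thin"), with the two lips allowed to differ. The next paragraph requires at least 42 subjects with FST IV–VI and continues: "This includes up to 21 subjects with FST V to VI who do not have to meet the inclusion criteria for MLFS".

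The exempt subjects are randomised, because SAP 1.1.2 makes FST V–VI a randomisation stratum. They also count toward the total: "Approximately 280 subjects will be randomized in a 2:1 ratio of treatment to control and treated" (Protocol 4.1), and "A maximum of 280 subjects will be treated in the study" (Protocol Synopsis, Statistical Methods).

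On size, SAP 1.1.2 randomises about 280 "to achieve a total sample size of 234 evaluable subjects". SAP 2.7 explains the step between the two figures: "Accounting for approximately 15% drop-outs and non-evaluable subjects due to protocol deviations at week 8, a total of approximately 280 subjects".

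On analysis sets, the ITT population "Includes all subjects who were randomized" (SAP 2.2), and a blacked-out passage follows those words. SAP 2.3.2 removes subjects from the PP set when key eligibility criteria are not met. The names of those criteria are blacked out, and the list of exclusions is stated not to be complete. Text is also blacked out directly after the 234 in SAP 1.1.2 and directly before the 15% sentence in SAP 2.7. Non-inferiority requires the two-sided 95% confidence interval to lie below 0.5 for both lips in both ITT and PP (SAP 2.1 and 2.4.3).

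**The concern.** The criterion these subjects may skip is on the scale that defines the primary endpoint, change in MLFS at week 8. Someone who starts with fuller lips may have less room to gain in either arm and so contribute little between-arm difference. In a non-inferiority trial that pulls the estimate in the favourable direction. Because the protocol permits the exemption, such a subject has arguably not deviated. The same subjects could then sit in both ITT and PP, and requiring success in both sets would not guard against the dilution.

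If these subjects are instead left out of the primary analysis, the 15% allowance appears not to cover them, since it is described in terms of drop-outs and deviations. The trial would then deliver fewer evaluable subjects than stated. On this view something needs correcting whichever way they are handled.

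**Working it through.** **Inputs.** From the documents: 280 randomised 2:1, up to 21 exempt, 234 evaluable, about 15% loss, margin 0.5, two-sided 95% interval. Assumed: the SD, because the planning SD is not visible.

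**1. The plan's own figure.** 234 / (1 − 0.15) = 275.3, so 276, which agrees with approximately 280. Forward, 280 × 0.85 = 238, at or above 234. The stated size reproduces.

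**2. Exempt subjects outside the primary analysis.**
- All 21 excluded and a further 15% lost: (280 − 21) × 0.85 = 259 × 0.85 = 220, which is 14 below 234.
- All 21 counted within the gap: 280 − 234 = 46, and 46 − 21 = 25 remain for other losses. 25/259 = 9.7%, so 234 is met with attrition up to that level.
- Ten exempt, with a further 15% lost: 270 × 0.85 = 229.5, within 2% of 234.
- Cost of 220 against 234 in per-lip power, assuming a true difference of 0 and an SD chosen so that 234 gives the named power: 95% becomes 93.8% (SD 1.0), 90% becomes 88.2% (SD about 1.11), 80% becomes 77.6% (SD about 1.29).

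**3. Exempt subjects inside both sets.** Let f be the exempt fraction and suppose those subjects show no between-arm difference.
- f = 21/280 = 0.075, and 0.5 × (1 − 0.075) = 0.4625, a shift of 0.0375 points.
- If all 21 remain among only 234, f = 21/234 = 0.090 and the difference is 0.455, a shift of 0.045.
- The true deficit in eligible subjects that would then sit on the margin is 0.5/0.925 = 0.541, or 0.549 with the larger f.

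One-sided error at the margin, per lip and per analysis set, is Φ(0.5f/SE − 1.96), with SE = SD × √(4.5/N) for 2:1 allocation. At N = 234 this is the same as SD × √(1/156 + 1/78).

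| Assumed SD | N = 234, f = 0.075 | N = 280, f = 0.075 | N = 234, f = 0.090 |
|---|---|---|---|
| 1.0 | 4.6% | 4.8% | 5.1% |
| 0.8 | 5.2% | 5.6% | 6.0% |
| 0.6 | 6.6% | 7.1% | 7.8% |

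The nominal value is 2.5%. If exempt subjects show half the difference, the first column becomes 3.4% (SD 1.0) to 4.1% (SD 0.6).

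**4. What the decision rule does to these figures.** Success needs both lips in both sets, so the trial-level error cannot exceed the smallest of the component errors. The table is therefore a ceiling. If exempt subjects are in ITT but not in PP, the PP test is undiluted and holds the overall error to about 2.5%.

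**The case for a change.** The best case for acting has four parts.

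- The two sentences in Protocol 4.1 are fully visible and conflict if read literally. This stands, but the second sentence is plainly an exception to the first, and nobody running the trial would conclude that the exempt subjects are barred.
- The visible description of the 15% does not name exempt subjects. This also stands, although non-evaluable can sensibly be read to include them, and the adjoining text is hidden.
- A subject whom the protocol exempts has not breached a criterion, so PP may keep that subject. This is possible but cannot be settled: the key criteria for PP exclusion are blacked out, and the list is open-ended.
- SAP 1.2.4 looks at consistency in FST IV–VI, where exempt subjects could be 21 of the minimum 42. This is a fair caution for reading an exploratory subgroup. It does not bear on the primary test.

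The dilution argument also stacks assumptions. The figure of 21 is a cap, and not having to meet the criterion is different from failing it. Some exempt subjects may score 1 or 2, and others may fall outside the range in one lip only. The upper end of the MLFS is not visible, so reduced room to improve is plausible but undocumented. The target indication shown in the Synopsis sets no fullness limit, so averaging over these subjects can be defended as a question in its own right.

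**Conclusion.** No change to the plan follows. The visible text establishes a clerical slip in Protocol 4.1, where a blanket statement is followed by its exception, and it places the exempt subjects inside the 280. It does not establish either harm.

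The shortfall to about 220 requires that the cap is filled, that all 21 are excluded, and that the full 15% is lost on top. The dilution requires that all 21 are in both ITT and PP and show no between-arm difference in either lip. Even then the shift is 0.0375 to 0.045 points against a margin of 0.5, and the error figures rest on an assumed SD. A consistent reading remains in which exempt subjects leave PP under the eligibility rule and count within the 15%. PP then guards against dilution and 234 is met with other attrition up to 9.7%.

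Restricting the primary sets to baseline MLFS 1 or 2 may repeat a rule that already stands in the blacked-out text. Restating 234 as 220 could introduce an error. The status of these subjects is a detail the SAP may already state; if it does not, analysts can settle it before database lock. This conclusion would weaken only if the unredacted SAP kept exempt subjects in both sets and their number approached the cap.
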